8.6.3 Vital Signs

Vital signs will be measured after 5 minutes of rest in a semi-supine position and will include temperature, systolic and diastolic blood pressure, and pulse.

8.6.4 Electrocardiograms

12-lead ECG(s) will be obtained after 5 minutes of rest in a semi-supine position. ECGs will be collected in triplicate using an ECG machine that automatically calculates the heart rate and measures PR, QRS, RR, QT intervals and morphological changes. A 1-minute rhythm strip will also be obtained to screen out participants with arrhythmias at baseline.

12-lead triplicate ECGs will be reviewed by an independent (blinded) reviewer for the purposes of assessing the safety endpoints of mean change from baseline QT interval corrected for heart rate, and any adverse events of special interest that would reflect a serious arrhythmia or suggest a potential for such arrhythmia.

8.6.5 Clinical Safety Laboratory Tests

Laboratory assessments, detailed in [Table 6: Protocol-required Safety Laboratory Tests](#), with the exception of urine pregnancy and drug tests, will be performed at the site clinical laboratory. Certificates and normal ranges will be stored in the site's Investigator Site File (ISF).

The site physician will confirm laboratory assessments gathered in screening for assessing eligibility. The site physician will use the list of normal ranges to conclude whether participants are eligible for the protocol and will indicate justification for admitting participants with abnormal values after consultation with the Medical Monitor.

Additional tests may be performed at any time during the study as determined necessary by the investigator or required by local regulations.

- If follow-up clinical labs are collected, record any clinically significant changes occurring during the study as an AE.
- All laboratory tests with values considered clinically significantly abnormal during participation in the study should be repeated until the values return to normal or baseline or are no longer considered clinically significant by the investigator or Medical Monitor.
 - If clinically significant values do not return to normal/baseline within a period of time judged reasonable by the investigator, the etiology should be identified, and the sponsor notified.
 - All protocol-required laboratory tests, as defined in [Table 6 Protocol-required Safety Laboratory Tests](#) must be conducted in accordance with the Laboratory Manual.
 - If laboratory values from non-protocol-specified laboratory tests performed at the institution's local laboratory require a change in participant management or are considered clinically significant by the investigator (e.g., SAE or AE or dose modification), then the results must be recorded.

An additional blood collection will be performed at the End of Study visit, which will only repeat Hematology, Clinical Chemistry, Routine Urinalysis and CPK. The maximum amount of blood collected from each participant over the duration of the study, including any extra assessments that may be required, will not exceed 500 mL.

Table 6: Protocol-required Safety Laboratory Tests

Laboratory Tests	Parameters
Hematology ^A	
• Hematocrit• Hemoglobin

	
 • Red Blood Cell (RBC) indices: 
 ○ RBC count ○ Percentage and absolute differential counts ○ Red cell distribution width (RDW) ○ Mean corpuscular volume (MCV) ○ Mean corpuscular hemoglobin (MCH) ○ Mean corpuscular hemoglobin concentration (MCHC) ○ % Reticulocytes • White blood cell (WBC) indices: 
 ○ RBC count ○ Percentage and absolute differential counts ○ Neutrophils ○ Lymphocytes ○ Monocytes ○ Eosinophils ○ Basophils
Clinical chemistry ^A	
 • Alanine aminotransferase (ALT)/serum glutamic-pyruvic transaminase (SGPT) • Albumin, serum • Albumin:Globulin (A:G) ratio • Alkaline phosphatase ^B • Aspartate aminotransferase (AST)/serum glutamic-oxaloacetic transaminase (SGOT) • Bilirubin, total and direct • Blood urea nitrogen (BUN): creatinine ratio • Calcium, serum • Carbon dioxide • Chloride, serum • Creatine phosphokinase (CPK) • Creatinine, serum and eGFR (calculated using CKD-EPI equation) • Globulin, total • Glucose • %CDT • Potassium, serum • Protein, total, serum • Sodium, serum
Routine urinalysis	
 • Specific gravity, color, appearance • pH, glucose, protein, blood, ketones, bilirubin, urobilinogen, nitrite, leukocyte esterase by dipstick
Pregnancy testing	
 • Highly sensitive urine human chorionic gonadotropin (hCG) pregnancy test (as needed for people able to become pregnant) ^B
Other screening tests	
 • Cytochrome P450 Genotyping Panel ^A • Thyroid Stimulating Hormone (TSH) with reflex free T3 and T4 • Urine drug screen • Urine or breath alcohol screen • Urine Nicotine/Cotinine screen

^A All screening and repeat samples may be taken in the non-fasted state.
 
^B Local urine testing will be standard for the protocol.
	

Investigators must document their review of each laboratory safety report.

8.6.6 Pregnancy Testing

- Pregnancy testing is required for participants that are a person able to become pregnant (PABP) as defined in [Appendix 2: Contraceptive and Barrier Guidance](#).
- Pregnancy testing should be conducted at the end of relevant systemic exposure.
- Additional serum or urine pregnancy tests may be performed, as determined necessary by the investigator or required by local regulation, to establish the absence of pregnancy at any time during the participant's participation in the study.

8.7 Adverse Events, Serious Adverse Events, and Other Safety Reporting

The investigator and any qualified designees are responsible for detecting, documenting, and recording events that meet the definition of an Adverse Event (AE) or Serious Adverse Event (SAE) and remain responsible for following up on all AEs.

AEs will be reported by the participant (or by a caregiver, surrogate, or the participant's legally authorized representative, when appropriate).

8.7.1 AE Definition

An AE is any untoward medical occurrence in a clinical study participant, temporally associated with the use of study intervention, whether or not considered related to the study intervention.

Note: An AE can therefore be any unfavorable and unintended sign (including an abnormal laboratory finding), symptom, or disease (new or exacerbated) temporally associated with the use of study intervention.

8.7.1.1 Events Meeting the AE Definition

- Any abnormal laboratory test results (hematology, clinical chemistry, or urinalysis) or other safety assessments (e.g., ECG, radiological scans, vital signs measurements), including those that worsen from baseline, considered clinically significant in the medical and scientific judgment of the investigator (i.e., not related to progression of any underlying disease).
- Exacerbation of a chronic or intermittent pre-existing condition including either an increase in frequency and/or intensity of the condition.
- New condition detected or diagnosed after study intervention administration even though it may have been present before the start of the study.
- Signs, symptoms, or the clinical sequelae of a suspected intervention-intervention interaction.
- Signs, symptoms, or the clinical sequelae of a suspected dosing error of either study intervention or a concomitant medication. A dosing error will not be reported as an AE/SAE unless it is an intentional overdose taken with possible suicidal/self-harming intent. Such overdoses should be reported regardless of sequelae.

8.7.1.2 Events NOT Meeting the AE Definition

- Any clinically significant abnormal laboratory findings or other abnormal safety assessments that are associated with an underlying disease, unless judged by the investigator to be more severe than expected for the participant's condition or meet other prespecified reporting criteria.

- Medical or surgical procedure (e.g., endoscopy, appendectomy): the condition that leads to the procedure may fit the criteria for an AE.
- Situations in which an untoward medical occurrence did not occur (social and/or convenience admission to a hospital).
- Anticipated day-to-day fluctuations of pre-existing disease(s) or condition(s) present or detected at the start of the study that do not worsen.
- Expressions of emotion or other emotional descriptions which are consistent with what would be expected during a typical IMP administration session with healthy volunteers, unless participant reports effects interfere with daily activities.
 - Limited examples of this include positive mood, compassion for self, compassion for others, intellectual efficiency, calmness, talkative, open to new experiences, and meaningful experience.

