8.7.3 Adverse Events of Special Interest (AESI)

In accordance with the guidance Clinical Safety Data Management Definitions and Standards for Expedited Reporting ICH Topic E2A: Guidance for Industry or FDA Safety Reporting Requirements for INDs and BA/BE Studies, the sponsor will pay special attention to a subset of AEs. These AEs will be marked in the eCRF with the denotation “Adverse Event of Special Interest” (AESIs) whether serious or non-serious.

A subset of AEs will be collected in order to assess signals of cardiovascular risk for the IMP in the intended patient population that could be indicative of QT interval prolongation or cardiac arrhythmias, including Torsade de pointes, sudden death, ventricular extrasystoles, ventricular tachycardia, ventricular fibrillation and flutter, non-postural syncope, and seizures.

A subset of AEs involving suicide risk will be collected as AESIs whether serious or non-serious. These AESI terms include:

- Suicides
- Suicide attempts
- Self-injurious behavior associated with suicidal ideation
- Suicidal ideation judged to be serious or severe in the opinion of the investigator

In order to assess signals of abuse potential for the IMP in the intended patient population:

- AESIs involving the terms of Behavioral addiction, Drug abuser, Substance abuser, Dependence, Intentional product misuse, Overdose (accidental, intentional, or prescribed), or Drug diversion in cases that are related to MDMA or “Ecstasy” (unregulated material presented as MDMA) will be collected and coded as AESIs in the eCRF.
- Cases of noncompliance, protocol violations, participants lost to follow-up, and any other reasons why participants dropped out of the study will be assessed for presence of AESIs;
- Qualitative urine drug test data will be collected prior to each Dosing Session. Any positive findings that cannot be attributed to pre-approved concomitant medications or diet will be reviewed by the Medical Monitor to assess compliance with ongoing eligibility criteria and for presence of AESIs.

If an AESI is a SAE or if it involves suicide risk, it should be reported via the eCRF within 24 hours of the site’s awareness of the event.

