8.7.6.2 Assessment of Severity

The investigator will assess severity for each AE and SAE reported during the study and assign it to one of the following categories:

- **Mild:** No limitation in normal daily activity.
- **Moderate:** Some limitation in normal daily activity.
- **Severe:** Unable to perform normal daily activity.

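### The last bullet of Protocol 8.7.1.2 can drop unfavourable but mild emotional effects from AE recording because they are expected, in conflict with 8.7.1 and 8.7.6.2

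*Protocol*

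**What the plan says.** Protocol 8.7.1 defines an AE as "any untoward medical occurrence in a clinical study participant, temporally associated with the use of study intervention, whether or not considered related", where the relation meant is a causal link with the drug. Its note adds: "An AE can therefore be any unfavorable and unintended sign". The note extends this to symptoms and diseases with the same timing. Neither sentence asks whether the effect was expected or whether it disturbed the participant's activities.

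The last bullet of 8.7.1.2 then lists among events that are not AEs: "Expressions of emotion or other emotional descriptions which are consistent with what would be expected during a typical IMP administration session with healthy volunteers". It allows a single exception, which depends on what the participant says: "unless participant reports effects interfere with daily activities". A sub-bullet then illustrates the rule: "Limited examples of this include positive mood, compassion for self, compassion for others, intellectual efficiency, calmness, talkative, open to new experiences, and meaningful experience".

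Section 8.7.6.2 has three severity grades. The lowest, mild, is "No limitation in normal daily activity".

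Table 2 (Section 3.0) makes AE incidence a safety endpoint under the objective on safety and tolerability in both fed and fasted states. Section 9.3.3 treats AE data descriptively.

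**The concern.** The exclusion works on two properties, expectedness and absence of reported interference, that the AE definition does not use. Its operative words cover emotional effects in general. The examples are pleasant or neutral, but they are offered only as examples, and the protocol names no list, such as a table in the Investigator's Brochure, against which expectedness is to be judged.

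If an unfavourable effect can be set aside because it is typical of an MDMA session, the AE tables understate how often participants had mild adverse emotional effects. The loss occurs at data collection, so no later analysis plan can restore those events. The study is open-label (Section 6.3) and the judgement of what is typical is left to the site, so two raters could treat the same episode differently.

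**Working it through.** The protocol states no AE rate, precision target or power for AE incidence, so there is no figure to reproduce. The check compares the text of the relevant sections.

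**1. When is an emotional effect recorded as an AE?**

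- Under 8.7.1: when it is untoward and temporally associated with the intervention.
- Under 8.7.1.2: if it is judged expected, only when the participant also reports interference with daily activities.

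**2. Add the severity scale.** Take interference (8.7.1.2) and limitation (8.7.6.2) as the same idea, which is the natural reading. For an effect that is unfavourable and follows dosing:

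| Judged expected? | Activity limited? | AE under 8.7.1 | Grade in 8.7.6.2 | Recorded under 8.7.1.2 |
|---|---|---|---|---|
| No | No | Yes | Mild | Yes |
| No | Yes | Yes | Moderate or severe | Yes |
| Yes | Yes, and reported | Yes | Moderate or severe | Yes |
| Yes | No | Yes | Mild | **No** |

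The last row is the conflict: the definition includes the event, the severity scale has a grade for it, and the exclusion removes it. For expected emotional effects the mild grade is unreachable.

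**3. Can an unfavourable emotional effect count as expected?** The protocol points both ways.

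- Table 1 (Section 2.3.1, Negative Psychological Impact) says anxiety or distress may arise during a session, then says that such effects are not anticipated in healthy volunteers.
- Section 4.3 anticipates that the chosen dose will bring out the full range of commonly reported MDMA effects.
- Section 8.5.2.1 draws its visual analogue scale (VAS) items from healthy-volunteer literature, and these include negative mood, confusion and emotional distress.

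A rater could cite the protocol for either answer.

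**4. How often can the exception operate?** Participants are confined from the night before dosing until 48 hours after it (Section 4.1) and sit or recline during the session (8.3.1.3). There is little normal activity to interfere with when the effects are strongest. The participant must report the interference, while 8.7.5 prefers open-ended, non-leading questions. After discharge the exception has more scope, because AE collection continues to study termination (8.7.4).

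**5. What do the examples cover?** The sub-bullet lists 8 effects. All 8 are among the 14 VAS items of 8.5.2.1. The other 14 − 8 = 6 items are 5 unfavourable ones (negative mood, body perception changes, confusion, difficulty concentrating, emotional distress) and one neutral one (social). None of the 5 unfavourable items is among the examples. The examples therefore suggest that favourable effects were in mind, but the operative sentence does not say so.

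**The case against.** The strongest reply is that the bullet only restates the definition. An AE must be untoward, and the note in 8.7.1 adds unfavourable and unintended. All eight examples are favourable or neutral, so they would not be AEs without the bullet. Table 1 says distress is not expected in this population, so on that text distress stays reportable. For the listed examples this reply is right. For the bullet as worded it is not enough: the list is open, the protocol contradicts itself on distress, and nothing confines the exclusion to effects that are not untoward.

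A reader might infer three stronger points, which the protocol does not support:

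- **That these effects go entirely unrecorded.** All eight examples are VAS items, as are negative mood and emotional distress. The VAS is taken once before dosing and at seven post-dose times, 1 + 7 = 8 times per session, up to 12 hours. It is an exploratory measure and does not produce an AE record, so it does not repair AE incidence, but the information is not lost altogether.
- **That the rule hides abuse-potential signals.** Section 8.7.3 defines that route by addiction, dependence, misuse, overdose and diversion terms, with review of dropouts and urine drug tests. It contains no mood term for the bullet to filter out.
- **That the fed/fasted comparison is biased in one direction.** The same rule applies in both periods. Fewer recorded emotional events would leave less to compare, but no direction follows from the text.

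**Conclusion.** The point holds in a limited form. As worded, the last bullet of 8.7.1.2 conflicts with 8.7.1 and 8.7.6.2. It allows unfavourable, mild emotional effects to be left off the AE record because they are expected, so AE incidence in each feeding state can be understated.

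This rests on two assumptions: that interference and limitation of activity mean the same thing, and that some raters will judge some unfavourable emotional effects to be expected. The protocol's mixed statements on distress leave room for the second.

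No size can be given. The protocol states no rate of emotional effects, and any numerical illustration would depend on an invented one. The understatement is confined to emotional terms, and the primary PK comparison is unaffected. It is still worth correcting before data collection, because it alters a safety endpoint in a way that cannot be undone afterwards.

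**What to change.** Reconcile 8.7.1, 8.7.1.2 and 8.7.6.2 in one of two ways.

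1. Delete the last bullet of 8.7.1.2 with its sub-bullet. Section 8.7.1 then governs, and effects that are not untoward stay outside AE recording by definition.
2. Keep the bullet but limit it to effects that are not untoward, with the eight present examples as a closed list. Add that any unfavourable emotional effect is recorded as an AE whether or not it is expected and whether or not it interferes with daily activities.

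Putting favourable or neutral effects on the AE form is not recommended: it would conflict with 8.7.1 and raise AE incidence with events that are not adverse.

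The cost is one bullet and matching CRF completion guidance. The downside is somewhat more mild AE entries and slightly higher reported AE rates.

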8.7.2 SAE Definition

An SAE is defined as any untoward medical occurrence that, at any dose, meets one or more of the criteria listed:

1. Results in death.
2. Is life threatening.
 - The term *life threatening* in the definition of SAE refers to an event in which the participant was at risk of death at the time of the event. It does not refer to an event, which hypothetically might have caused death, if it were more severe.
3. Requires inpatient hospitalization or prolongation of existing hospitalization.
 - In general, hospitalization signifies that the participant has been admitted (usually involving at least an overnight stay) at the hospital or emergency ward for observation and/or treatment that would not have been appropriate in the physician's office or outpatient setting. Complications that occur during hospitalization are AEs. If a complication prolongs hospitalization or fulfills any other serious criteria, the event is serious. When in doubt as to whether hospitalization occurred or was necessary, the AE should be considered serious.
 - Hospitalization for elective treatment of a pre-existing condition that did not worsen from baseline is not considered an AE.
4. Results in persistent or significant disability/incapacity.
 - The term disability means a substantial disruption of a person's ability to conduct normal life functions.
 - This definition is not intended to include experiences of relatively minor medical significance such as uncomplicated headache, nausea, vomiting, diarrhea, influenza, and accidental trauma (e.g., sprained ankle) that may interfere with or prevent everyday life functions but do not constitute a substantial disruption.
5. Is a congenital anomaly/birth defect.
6. Other situations:
 - Medical or scientific judgment should be exercised by the investigator in deciding whether SAE reporting is appropriate in other situations such as significant medical events that may jeopardize the participant or may require medical or surgical intervention to prevent one of the other outcomes listed in the above definition. These events should usually be considered serious.

8.7.3 Adverse Events of Special Interest (AESI)

In accordance with the guidance Clinical Safety Data Management Definitions and Standards for Expedited Reporting ICH Topic E2A: Guidance for Industry or FDA Safety Reporting Requirements for INDs and BA/BE Studies, the sponsor will pay special attention to a subset of AEs. These AEs will be marked in the eCRF with the denotation “Adverse Event of Special Interest” (AESIs) whether serious or non-serious.

A subset of AEs will be collected in order to assess signals of cardiovascular risk for the IMP in the intended patient population that could be indicative of QT interval prolongation or cardiac arrhythmias, including Torsade de pointes, sudden death, ventricular extrasystoles, ventricular tachycardia, ventricular fibrillation and flutter, non-postural syncope, and seizures.

A subset of AEs involving suicide risk will be collected as AESIs whether serious or non-serious. These AESI terms include:

- Suicides
- Suicide attempts
- Self-injurious behavior associated with suicidal ideation
- Suicidal ideation judged to be serious or severe in the opinion of the investigator

In order to assess signals of abuse potential for the IMP in the intended patient population:

- AESIs involving the terms of Behavioral addiction, Drug abuser, Substance abuser, Dependence, Intentional product misuse, Overdose (accidental, intentional, or prescribed), or Drug diversion in cases that are related to MDMA or “Ecstasy” (unregulated material presented as MDMA) will be collected and coded as AESIs in the eCRF.
- Cases of noncompliance, protocol violations, participants lost to follow-up, and any other reasons why participants dropped out of the study will be assessed for presence of AESIs;
- Qualitative urine drug test data will be collected prior to each Dosing Session. Any positive findings that cannot be attributed to pre-approved concomitant medications or diet will be reviewed by the Medical Monitor to assess compliance with ongoing eligibility criteria and for presence of AESIs.

If an AESI is a SAE or if it involves suicide risk, it should be reported via the eCRF within 24 hours of the site’s awareness of the event.

8.7.4 Time Period and Frequency for Collecting AE and SAE Information

All SAEs will be collected from the signing of the ICF until the study termination visit.

All AEs will be collected from initial study enrollment (in participants who meet eligibility criteria following screening) until the study termination visit.

Medical occurrences that begin prior to randomization but after obtaining informed consent will be recorded as medical history/current medical conditions, not as AEs.

All SAEs will be recorded and reported to the sponsor or designee immediately and under no circumstance should this exceed 24 hours. The investigator will submit any updated SAE data to the sponsor within 24 hours of it being available.

Investigators are not obligated to actively seek information on AEs or SAEs after conclusion of the study participation. However, if the investigator learns of any SAE, including a death, at any time after a participant has been discharged from the study, and they consider the event to be reasonably related to the study intervention or study participation, the investigator must promptly notify the sponsor.

